Appendix 14 Menstruation Diary

Study Number: Subject Number:
Site Number: Date of Study Enrollment:

Each row represents a day of the month. Please count the number of sanitary pads and/or tampons you used each day (24 hours period), if any. The light, medium, and heavy columns indicate how stained each item was with blood. If you used both a pad and tampon simultaneously and both sanitary items were stained with blood, please include both items in the diary.

If you passed any clots, please indicate this on the relevant days and the approximate size (small = close to the size of penny; large = close to the size of a quarter).

If you experienced any episodes of 'flooding' / overflowing / staining of clothing or underwear, please indicate the number of episodes on the relevant days.

If you also experienced bleeding between periods that required sanitary protection, please record the items on the relevant days.

Please do not write anything in the Score column.

Date	Pads			Tampons			Clots		Flooding Episodes	Score
	Light	Medium	Heavy	Light	Medium	Heavy	Small	Large		TO BE COMPLETED BY STUDY STAFF ONLY
1										
2		ļ.								
3										-
4		\\								
5								2		
6		k								
7										
8										
- 922										
10 11										
12										
14										
15										
16		4		4:						-
17										
18		1		-				-		
19										
20		/		1/2				2		
21		2								
22										
23									¢.	
24										
25								5 3		
26										
27										
28				· ·						
29		ř.		Ť ·						
30										
31

Hemophilia A is most commonly caused by an inherited FVIII gene mutation within the Xq28 region of the X chromosome. It occurs almost exclusively in males with one defective copy of the relevant gene on their X chromosome. Females who are carriers of hemophilia A may experience bleeding symptoms similar to those seen in men with mild hemophilia A, as approximately 10% of carriers have a FVIII activity less than 35% (Plug et al. 2006). Rarely, women can have more severe bleeding symptoms requiring treatment and may develop FVIII inhibitors. Approximately 30% of patients with hemophilia A do not have a family history of the disorder; these cases arise from spontaneous FVIII gene mutations. The severity of the disease roughly correlates with the residual endogenous level of FVIII activity. However, classifying patients into mild, moderate and severe categories based on the residual FVIII levels alone has been called into question. Recent guidance now recommends classification incorporating treatment strategies (e.g., prescribing prophylaxis vs. on-demand regimens based on bleeding phenotype).

Emicizumab (also known as ACE910, RO5534262, and HEMLIBRA®) is a recombinant, humanized, bispecific, immunoglobulin G4 monoclonal antibody that binds with moderate affinity to activated factor IX (FIXa) and factor X (FX), mimicking the co-factor function of FVIII. Based on the Phase III program, emicizumab gained approval in many countries, including the United States and the European Union (EU) and is indicated for routine prophylaxis to prevent bleeding or reduce the frequency of bleeding episodes in adults and children with hemophilia A (congenital FVIII deficiency) with or without FVIII inhibitors and can be used in all age groups. In the EU however, the non-inhibitor label is restricted to patients with severe hemophilia A (FVIII level < 1%).

To investigate emicizumab prophylaxis in patients with mild or moderate hemophilia A, this study will evaluate the safety, efficacy, pharmacokinetics, and pharmacodynamics of emicizumab in patients with mild (FVIII level between > 5% and < 40%) or moderate hemophilia A (FVIII level between \geq 1% and \leq 5%) without inhibitors against FVIII whose bleeding phenotype warrants prophylactic treatment.

2. STUDY DESIGN

Study BO41423 is a multicenter, open-label, single-arm study designed to evaluate the safety, efficacy, pharmacokinetics, and pharmacodynamics of emicizumab in patients with mild or moderate hemophilia A without inhibitors against FVIII. Four loading doses of emicizumab 3 mg/kg will be administered subcutaneously once weekly (QW) for

[figure not shown]
Emicizumab — F. Hoffmann-La Roche Ltd 4/Statistical Analysis Plan BO41423

4 weeks followed by patient preference of one of the following maintenance regimens: 1.5 mg/kg QW, 3 mg/kg every 2 weeks (Q2W), or 6 mg/kg every 4 weeks (Q4W). The three maintenance dose regimens have shown equivalent average steady-state exposure, and demonstrated consistent efficacy and safety, and are approved in several countries for the treatment of hemophilia A with or without FVIII inhibitors. As patients with mild or moderate hemophilia A have residual FVIII levels of ≥ 1%, it is of interest to collect safety data over a longer time period.

Approximately 70 patients of all age groups will be enrolled, approximately 20 patients with mild (FVIII level between > 5% and < 40%) and 50 patients with moderate (FVIII level between \geq 1% and \leq 5%) hemophilia A, without FVIII inhibitors whose bleeding phenotype warrants prophylaxis.

Each patient (or their legally authorized representative herein referred to as patient[s]) will choose the preferred emicizumab maintenance regimen (1.5 mg/kg SC QW, 3 mg/kg SC Q2W, or 6 mg/kg SC Q4W) after consultation with his or her treating physician. The chosen regimen needs to be maintained throughout the study until completion of at least 52 weeks. All patients with suboptimal control of bleeding as defined by the protocol will be offered the option to increase their emicizumab maintenance dose to 3 mg/kg QW, with approval from the Medical Monitor.

Figure 1 Study Schema

QW = once a week; Q2W = every 2 weeks; Q4W = every 4 weeks.

Note: Patients who discontinue study drug prior to end of study will return to the clinic for a safety follow-up visit 24 weeks after the final dose of study drug.

a Interim data reviews will be performed at 24 weeks.

The total length of the study, from screening of the first patient to the end of the study, is expected to be approximately 27 months depending on the recruitment rate

2.1 PROTOCOL SYNOPSIS

The Protocol Synopsis is in Appendix 1.

Emicizumab —F. Hoffmann-La Roche Ltd 5/Statistical Analysis Plan BO41423

2.2 COLLECTION OF PATIENT-REPORTED DATA

2.2.1 Collection of Bleed and Medication Data

Bleed and medication data are collected through an electronic bleed and medication questionnaire (BMQ), which was developed by the Sponsor given that no standard questionnaire for collection of these data exists.

Patients (or their legally authorized representative) will complete a BMQ whenever a bleed occurs or at least on a weekly basis (retrospective reporting for last 7 days) via an electronic, handheld device. For each bleed episode, the patient will provide information regarding bleed start date and time, reason, type, location, and associated symptoms (only collected for muscle and joint bleeds in patients 12 years of age and older). Hemophilia medications and reason for treatment (e.g., bleed, surgery, physical activity) will also be collected through the use of the BMQ. If the electronic, handheld device is not available, a paper questionnaire might be used. Investigators will review the bleed and bleed medication data as per the schedule of activities and will have the option to correct or complete the BMQ in agreement with the patient via a Data Request Form process or via a web-based portal, once implemented. Patients who withdraw from emicizumab treatment will continue to record bleeds and hemophilia medication administration until they complete the safety follow-up visit.

2.2.2 Collection of Health-Related Quality-of-Life Data

At specified visits, patients will complete health-related quality-of-life (HRQoL), health status, and satisfaction/preference questionnaires on a tablet device that will remain at study sites. The instructions for completing the patient-reported outcome (PRO) questionnaires electronically will be provided by the investigator staff during the Week 1 visit at the site. The data will be transmitted automatically after entry to a centralized secure database at the vendor.

Comprehensive Assessment Tool of Challenges in Hemophilia (CATCH) is a newly developed, validated instrument to measure the effect of hemophilia and its treatment on pediatric (aged 8–17 years) and adult patients (aged ≥ 18 years), and caregivers of pediatric patients. The adult and pediatric versions of CATCH are composed of seven domains, and the caregiver version of CATCH is composed of two domains. Each domain constitutes a set of specific items and overall items that help to assess the overall impact of the disease on a given domain. The current versions of the CATCH can be administered electronically. The items in the CATCH versions are scored on ordinal scales (3–4 points for pediatric version, 4–5 points for adults and caregiver versions), with an 11-point numeric rating scale for pain. All CATCH raw scores are obtained by calculating the mean of the item scores for all items within the corresponding concept and applying a linear transformation. The transformed scores range from 0 to 100 scale with higher scores indicating higher perceived risk or effect.

Emicizumab —F. Hoffmann-La Roche Ltd 6/Statistical Analysis Plan BO41423

2.2.3 Collection of Activity Data

Patients (≥ 5 years of age) should wear the study device continuously (24 hr/day) every day for designated 2-week periods during the study (see Appendix 1) as follows: Weeks 1–2, Weeks 12–13, Weeks 24–25, Weeks 36–37, and Weeks 48–49. Patients will be instructed to wear the accelerometer on the wrist for 14 consecutive days. Patients will be instructed to charge the device.

Accelerometry data will be collected passively using the study device and uploaded regularly to provide continuous measures of, but not limited to, moderate to vigorous physical activity (MVPA) and daily step count (DSC); in addition, further analyses may be performed.

An activity count is a measure of the acceleration that is measured by the device. The number of hours the device is worn each day will also be derived from the activity counts data.

2.3 OBJECTIVES AND ENDPOINTS

2.3.1 Primary Efficacy Objective

The primary efficacy objective for this study is to evaluate the efficacy of emicizumab on the basis of the following endpoint:

• Number of treated bleeds over time (i.e., bleed rate)

2.3.2 Secondary Efficacy Objective

The secondary efficacy objective for this study is to evaluate the efficacy of emicizumab on the basis of the following endpoints:

- Number of all bleeds (i.e., those treated and untreated with FVIII) over time
- Number of joint bleeds over time
- Number of target joint bleeds over time (target joints are defined as joints with
 ≥ 3 bleeds occurring in the same joint during the last 24 weeks)
- Number of spontaneous bleeds over time (spontaneous bleed rate)
- Joint health, as assessed through use of the Hemophilia Joint Health Score (HJHS) at specified timepoints
- Health-related quality of life (HRQoL), as assessed through use of the CATCH Questionnaire over time
- Preference for emicizumab compared with previous FVIII regimen, as assessed through use of the Emicizumab Preference Survey (EmiPref) at Week 17
- Effect of emicizumab prophylaxis treatment on physical activity compared with physical activity at baseline
- Effect of emicizumab prophylaxis treatment on menstruation heaviness and menstruation-related quality of life in female patients of childbearing potential, as assessed through the use of the Menstrual Bleeding Questionnaire (MBQ) and the

Emicizumab —F. Hoffmann-La Roche Ltd 7/Statistical Analysis Plan BO41423

Menstruation Diary (MD) with the Pictorial Blood Assessment Chart (PBAC) over time

2.3.3 Pharmacokinetic Objectives

The Pharmacokinetic (PK) objective for this study is to characterize the emicizumab PK profile on the basis of the following endpoint:

• Plasma concentration of emicizumab at specified timepoints

2.3.4 Safety Objectives

The safety objective for this study is to evaluate the safety profile of emicizumab in patients with non-severe hemophilia A without inhibitors on the basis of the following endpoints:

- Incidence and severity of adverse events, with severity determined according to WHO Toxicity Grading Scale
- Incidence of thromboembolic events
- Incidence of thrombotic microangiopathy (TMA)
- Change from baseline in physical examination findings
- Change from baseline in and vital signs
- Change from baseline in ECG parameters
- Incidence of laboratory abnormalities
- Incidence and severity of injection-site reactions
- Incidence of adverse events leading to drug discontinuation
- Incidence of severe hypersensitivity, anaphylaxis, and anaphylactoid events
- Incidence and significance of anti-emicizumab antibodies
- Incidence of de novo development of FVIII inhibitors

2.3.5 Immunogencity Objectives

The immunogenicity objective for this study is to evaluate the immune response to emicizumab on the basis of the following endpoints:

- Prevalence of anti-drug antibodies (ADAs) at baseline and incidence of ADAs during the study
- Number and proportion of patients who develop anti-FVIII inhibitors (titer≥ 0.6 BU/mL) at specified timepoints

2.3.6 Biomarker Objective

The exploratory biomarker objective for this study is to investigate the effect of emicizumab on pharmacodynamic (PD) parameters, including but not limited to thrombin generation, FVIII activity, FVIII protein, D-dimer, and prothrombin fragment 1 + 2 (PF1 + 2) at regular intervals throughout the study and at times of treated bleeds. Changes over time in biomarkers related to bone and joint health may also be explored.

Emicizumab — F. Hoffmann-La Roche Ltd 8/Statistical Analysis Plan BO41423

2.3.7 Health Status Utility Objective

The exploratory health status utility objective for this study is to evaluate health status utility scores of patients treated with emicizumab on the basis of the following endpoint:

• Change from baseline in EuroQol 5-Dimension 5-level Questionnaire (EQ-5D-5L) index utility and visual analog scale (VAS) scores at specified timepoints

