The safety objective for this study is to evaluate the safety profile of emicizumab in patients with non-severe hemophilia A without inhibitors on the basis of the following endpoints:

- Incidence and severity of adverse events, with severity determined according to WHO
 Toxicity Grading Scale
- Incidence of thromboembolic events
- Incidence of thrombotic microangiopathy
- Change from baseline in physical examination findings
- Change from baseline in and vital signs
- Change from baseline in ECG parameters
- Incidence of laboratory abnormalities
- Incidence and severity of injection-site reactions
- Incidence of adverse events leading to drug discontinuation
- Incidence of severe hypersensitivity, anaphylaxis, and anaphylactoid events
- Incidence and significance of anti-emicizumab antibodies
- Incidence of de novo development of FVIII inhibitors

Emicizumab—F. Hoffmann-La Roche Ltd

13/Protocol BO41423, Version 3

Efficacy Objectives

Primary Efficacy Objective

The primary efficacy objective for this study is to evaluate the efficacy of emicizumab on the basis of the following endpoint:

Number of treated bleeds over time (i.e., bleed rate)

Secondary Efficacy Objectives

The secondary efficacy objective for this study is to evaluate the efficacy of emicizumab on the basis of the following endpoints:

- Number of all bleeds (i.e., those treated and untreated with FVIII) over time
- Number of joint bleeds over time
- Number of target joint bleeds over time (target joints are defined as joints with ≥3 bleeds occurring in the same joint during the last 24 weeks or unresolved target joints)

An unresolved target joint is defined as a target joint that does not fulfill the criterion of ≤ 2 bleeds into this joint within a consecutive 12-month period.

- Number of spontaneous bleeds over time (spontaneous bleed rate)
- Joint health, as assessed through use of the Hemophilia Joint Health Score at specified timepoints
- Health-related quality of life (HRQoL), as assessed through use of the Comprehensive Assessment Tool of Challenges in Hemophilia (CATCH) Questionnaire over time
- Preference for emicizumab compared with previous FVIII regimen, as assessed through use of the Emicizumab Preference Survey (EmiPref) at Week 17
- Effect of emicizumab prophylaxis treatment on physical activity compared with physical activity at baseline

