2.2 EFFICACY OBJECTIVES

2.2.1 Primary Efficacy Objective

The primary efficacy objective for this study is to evaluate the efficacy of emicizumab on the basis of the following endpoint:

• Number of treated bleeds over time (i.e., bleed rate)

2.2.2 Secondary Efficacy Objectives

The secondary efficacy objective for this study is to evaluate the efficacy of emicizumab on the basis of the following endpoints:

- Number of all bleeds (i.e., those treated and untreated with FVIII) over time
- Number of joint bleeds over time
- Number of target joint bleeds over time (target joints are defined as joints with ≥3 bleeds occurring in the same joint during the last 24 weeks or unresolved target joints)

An unresolved target joint is defined as a target joint that does not fulfil the criterion of ≤ 2 bleeds into this joint within a consecutive 12-month period.

- Number of spontaneous bleeds over time (spontaneous bleed rate)
- Joint health, as assessed through use of the Hemophilia Joint Health Score (HJHS) at specified timepoints
- Health-related quality of life (HRQoL), as assessed through use of the Comprehensive Assessment Tool of Challenges in Hemophilia (CATCH) Questionnaire over time
- Preference for emicizumab compared with previous FVIII regimen, as assessed through use of the Emicizumab Preference Survey (EmiPref) at Week 17
- Effect of emicizumab prophylaxis treatment on physical activity compared with physical activity at baseline
- Effect of emicizumab prophylaxis treatment on menstruation heaviness and menstruation-related quality of life in female patients of childbearing potential, as assessed through the use of the Menstrual Bleeding Questionnaire (MBQ) and the Menstruation Diary (MD) with the Pictorial Blood Assessment Chart (PBAC) over time

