4. MATERIALS AND METHODS

4.1 PATIENTS

Approximately 70 patients of all age groups will be enrolled in the study consisting of approximately 20 patients with mild and approximately 50 patients with moderate hemophilia A without FVIII inhibitors whose phenotype warrants prophylaxis.

4.1.1 Inclusion Criteria

Patients must meet the following criteria for study entry:

- Signed Informed Consent Form (signed by patient's legally authorized representative for patients who have not attained the age of majority)
- Signed Assent Form when appropriate, as determined by patient's age and individual site and country standards
- Willingness and ability to comply with schedules visits, treatment plans, laboratory tests and other study procedures
- Diagnosis of mild (FVIII level between > 5% and < 40%) or moderate (FVIII level between ≥ 1% and ≤ 5%) congenital Hemophilia A without FVIII inhibitors
- Weight ≥3 kg
- Need for prophylaxis based on investigator assessment
- A negative test for inhibitor (i.e., <0.6 BU/mL) within 8 weeks prior to enrollment
- No documented inhibitor (i.e., < 0.6 BU/mL), FVIII half-life < 6 hours, or FVIII recovery < 66% in the last 5 years

Patients who completed successful immune tolerance induction (ITI) at least 5 years before screening are eligible, provided they have had no evidence of inhibitor recurrence (permanent or temporary) as may be indicated by a detection of an inhibitor, FVIII half-life <6 hours or FVIII recovery <66% since completing ITI (Antun et al. 2015).

Emicizumab—F. Hoffmann-La Roche Ltd 35/Protocol BO41423, Version 3

- Documentation of the details of prophylactic or episodic FVIII treatment and of number of bleeding episodes for at least the last 24 weeks prior to enrollment
- Adequate hematologic function, defined as platelet count ≥100,000 cells/µL and hemoglobin ≥8 g/dL (4.97 mmol/L) at the time of screening
- Adequate hepatic function defined as total bilirubin ≤1.5×age-adapted upper limit of normal (ULN) (excluding Gilbert syndrome) and both AST and ALT ≤3×age-adapted ULN at the time of screening, and no clinical signs or known laboratory/radiographic evidence consistent with cirrhosis
- Adequate renal function, defined as serum creatinine ≤2.5 × age-adapted ULN and creatinine clearance ≥30 mL/min by Cockroft-Gault formula
- For women of childbearing potential: agreement to remain abstinent (refrain from heterosexual intercourse) or use contraception as defined below:

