4.5.1 Informed Consent Forms and Screening Log

Written informed consent/assent for participation in the study must be obtained before performing any study-related procedures (including screening evaluations). Informed Consent/Assent Forms for enrolled patients and for patients who are not subsequently enrolled will be maintained at the study site.

All screening evaluations must be completed and reviewed to confirm that patients meet all eligibility criteria before enrollment. The investigator will maintain a screening log to record details of all patients screened and to confirm eligibility or record reasons for screening failure, as applicable.

Emicizumab—F. Hoffmann-La Roche Ltd 43/Protocol BO41423, Version 3

4.5.2 Medical History, Concomitant Medication, and Demographic Data

Medical history, including clinically significant diseases, procedures, use of alcohol and drugs of abuse within the past year, and medical allergies will be recorded at baseline. In particular, sites should record whether the patient has any history of prior ITI, anaphylaxis, or known thrombophilia. For female patients, fertility status, and menstruation and menorrhagia history data will be recorded at baseline. In addition, all medications (including prescription, over-the-counter, and herbal/homeopathic remedies and therapies) used by the patient within 4 weeks prior to enrollment will be recorded. All bleed information (i.e., start date, cause, type, location) during the 24 weeks prior to study entry should be documented.

Demographic data will include age, sex, and self-reported race/ethnicity. Race and ethnicity are standard data points in clinical trials conducted by Roche, collected as part of the demographics, as there is potential that diseases might affect racial groups differently.

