4.5.7.4 Bleed Definitions and Reporting Definition of a Bleed

For the purpose of the efficacy analyses, a standardized definition of bleed, adapted from criteria defined by the Subcommittee on Standards and Criteria, FVIII/Factor IX subcommittee of the International Society of Thrombosis and Hemostasis, and similar to that used in a recent clinical study, will be used in this study (Blanchette et al. 2014; Mahlangu et al. 2014) as follows:

- An event is considered a treated bleed if coagulation factors are administered to treat signs or symptoms of bleeding (e.g., pain, swelling). An additional definition of all reported bleeds (irrespective of treatment with coagulation factors) will be applied for a separate analysis.
- Bleeds starting from the first sign of bleed and ending 72 hours after the last treatment for the bleed, within which any symptoms of bleeding at the same location or injections are ≤72 hours apart, are considered the same bleed.
- Any injection to treat the bleed, taken > 72 hours after the preceding injection, is considered the first injection to treat a new bleed at the same location.
- Any bleed at a different location is considered a separate bleed regardless of time from last injection.

Definition of Bleed Sites

Bleed sites are defined as follows:

Target joints: defined as a major joint (e.g., hip, elbow, wrist, shoulder, knee, and ankle) into which repeated bleeds occur (frequency of ≥ 3 bleeds into the same joint over the last 24 weeks prior to study entry) or as an unresolved target joint. An unresolved target joint is defined as a target joint that does not fulfil the criterion of ≤ 2 bleeds into this joint within a consecutive 12-month period (Blanchette et al. 2014).

Emicizumab—F. Hoffmann-La Roche Ltd 51/Protocol BO41423, Version 3

- Joint bleeds: defined as bleeds with bleed type "joint bleed" reported via the BMQ with at least one of the following symptoms:
 - Increasing swelling or warmth of the skin over the joint
 - Increasing pain
 - Progressive loss of range of motion or difficulty in using the limb as compared with baseline
- Muscle bleeds (sites as per the BMQ)
- Other (sites as per the BMQ)

Definitions of Bleed Types

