3.3.2.1 Bleed Rate

The efficacy of emicizumab is characterized by the number of bleeds over time. This will be calculated using a negative binomial (NB) regression model, which accounts for different follow-up times, with time that each patient stays in the study (efficacy period) included as an offset in the model. In addition, the number of bleeds will also be annualized for each patient using the following formula:

Annualized bleed rate (ABR) = (Number of bleeds/number of days during the efficacy period) \times 365.25.

The mean and median ABR based on the above formula using the observed numbers of bleeds instead of the number resulting from the model will also be calculated. In the case where the negative binomial model does not converge, the alternative derivations of the ABR will be used as the sole method of analysis.

ABR corresponding to treated bleeds, all bleeds, treated joint bleeds, treated target joint bleeds, and treated spontaneous bleeds will be analyzed in a similar manner. These will be summarized for all patients and listed for each patient individually. Several exploratory analyses will be conducted to characterize the type, location, and frequency.

3.3.2.1.1 72-Hour Rule:

Two bleeds of the same type (e.g., "joint", "muscle", or "other") and at the same anatomical location are considered to be one bleed if the second bleed occurs within 72 hours from the last treatment for the first bleed. The last treatment is defined as the last treatment before a new bleed occurs, either in the same or in a different location.

Bleeding rates and characteristics of bleeding describing location and type will also be provided using the 72-hour rule.

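### The SAP's target-joint definition lacks the protocol's unresolved limb and its major-joint and study-entry limits, so the target-joint bleed rate and subgroup can misclassify joints

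*SAP*

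**What the plan says.** SAP 2.3.2 lists target joint bleeds as a secondary endpoint and defines a target joint by one condition: at least "3 bleeds occurring in the same joint during the last 24 weeks". The term is then used twice without further definition. SAP 3.3.2.1 says that "treated target joint bleeds, and treated spontaneous bleeds will be analyzed in a similar manner" to the other bleed rates. SAP 3.3.3 splits the treated-bleed and all-bleed ABRs by whether a patient had any target joint at study entry.

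Protocol version 3 gives two alternative conditions in three places. Section 2.2.2 has at least three "bleeds occurring in the same joint during the last 24 weeks or unresolved target joints". The synopsis says the same and adds: "An unresolved target joint is defined as a target joint that does not fulfill the criterion" of at most two bleeds in a consecutive 12-month period. Section 4.5.7.4, which holds the bleed definitions, limits target joints to major joints and counts bleeds "over the last 24 weeks prior to study entry) or as an unresolved target joint". It describes the second kind as a target joint that "does not fulfil the criterion of ≤ 2 bleeds into this joint within a consecutive 12-month period".

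On data, protocol 4.5.2 says that bleed details "during the 24 weeks prior to study entry should be documented", and inclusion criterion 4.1.1 requires documentation of the "number of bleeding episodes for at least the last 24 weeks prior to enrollment".

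**The concern.** Two current documents define one endpoint differently, and the SAP is the one that will be programmed. The word unresolved does not occur in the SAP, so 2.3.2 is its operative rule.

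Two outputs depend on it. The target-joint ABR would omit bleeds into joints that qualify only by the unresolved limb. The target-joint subgroup would place patients whose only target joints are unresolved in the no-target-joint level, and both treated-bleed and all-bleed ABRs are summarized by that split. Each result would carry the protocol's label without meeting the protocol's definition.

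The likely cause is version lag. SAP Appendix 1 reproduces the synopsis of protocol version 2, which has the same one-condition wording. SAP Appendix 2 shows the same lag elsewhere: its joint-score footnote lacks the age limit of 4 years found in version 3, and its footnote on prior FVIII names a different case report form page.

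**Working it through.** The plan states no figure on this point, so there is nothing to reproduce. The check compares the definitions and then tests whether they can classify the same joint differently.

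**1. Definitions side by side**

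| Element | SAP 2.3.2 | Protocol synopsis and 2.2.2 | Protocol 4.5.7.4 |
|---|---|---|---|
| At least 3 bleeds in 24 weeks | yes | yes | yes |
| Or unresolved target joint | no | yes | yes |
| Major joints only | no | no | yes |
| 24 weeks tied to study entry | no | no | yes |
| When unresolved status is judged | not applicable | not stated | not stated |

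**2. Joints that the protocol counts and the SAP does not** (constructed examples, weeks relative to entry)

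- Bleeds at −48, −40 and −30. The span is −30 − (−48) = 18 weeks, so the joint became a target joint at week −30. Only 30 weeks have passed since, and the last 12 months hold 3 bleeds, so it is unresolved. Bleeds in the last 24 weeks: 0. Protocol yes, SAP no.
- Bleeds at −50, −44, −36 and −10. The first three span 14 weeks. The last 52 weeks hold 4 bleeds and the last 24 weeks hold 1. Protocol yes, SAP no.

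**3. Joints that the SAP counts and protocol 4.5.7.4 does not**

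- A joint that is not a major joint, with 3 bleeds in the 24 weeks before entry. It meets SAP 2.3.2 but falls outside the major-joint limit.
- A joint that first reaches 3 bleeds in 24 weeks during the study. If the SAP's window is read as rolling, it counts; the first limb of 4.5.7.4 excludes it. This reading is open only for the ABR, because SAP 3.3.3 ties the subgroup to study entry.

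**4. Effect on the rate**

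For each patient, ABR = (bleeds / days in efficacy period) × 365.25. The definition changes the numerator only. Dropping the unresolved limb alone removes bleeds or removes none, so each patient's observed target-joint ABR, and hence its mean and median, stays the same or falls. The negative binomial estimate has no such simple formula when follow-up differs. In 300 simulated datasets of 70 patients with unequal follow-up (assumed inputs), adding bleeds never lowered it. The gaps in step 3 add bleeds, so they push the other way.

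**5. Status changes with time**

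Take the joint with bleeds at −48, −40 and −30 and none later. Just over 4 weeks after entry, the bleed at −48 drops out of the preceding 12 months (48 + 4 = 52 weeks). Two bleeds remain, and the joint then meets the resolution criterion. Whether its on-study bleeds count therefore depends on when status is judged, which no document states.

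**6. Scale**

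The documents give no bleed rate per joint. The nearest figure is in protocol 1.1: a UK national database report on moderate hemophilia A with a median ABR of 3 (1.0–7.0), all sites combined. Over 24 weeks (168 / 365.25 = 0.46 years) that is 3 × 0.46 ≈ 1.4 bleeds at the median and 7 × 0.46 ≈ 3.2 at the upper figure, spread over every location. If trial patients are similar, target joints would be few under either definition. How many would be unresolved only cannot be derived.

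**The case against.** The best defence of the SAP is practical. Itemized bleed history is required for 24 weeks only, so the SAP's single condition is the one that the planned data support. The second limb needs a 12-month view and knowledge of earlier target-joint status, and neither document names a per-joint source for it. That limitation is real, and part of it lies in the protocol. But the SAP does not present its rule as a reasoned narrowing, and the inclusion criterion asks for at least 24 weeks, so longer history may exist for some patients. If the limb cannot be assessed, the SAP should say so and not leave it out silently.

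It is also fair that this is a secondary endpoint in a study without hypothesis tests, and that SAP 3.3.3 already warns about small subgroups. These points limit the consequence but do not reconcile the texts.

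The protocol is not fully consistent either: its synopsis and 2.2.2 share the SAP's looser wording on joint type and window. That is a reason to settle on 4.5.7.4 explicitly.

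Finally, only the version 2 synopsis is available, not the version 2 body. The version-lag explanation is confirmed at synopsis level only.

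**Conclusion.** The mismatch is real and should be corrected. SAP 2.3.2 omits a limb that version 3 states three times, and it also lacks the major-joint limit and study-entry anchor of 4.5.7.4. The target-joint ABR and the target-joint subgroup can therefore misclassify joints and patients. The primary treated-bleed rate and the overall all-bleeds rate do not use the definition, and no test is affected.

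A reader might infer that the SAP can only make the target-joint endpoint look better. The documents do not support that. It would follow if the SAP's target joints were a subset of the protocol's, but the missing major-joint and study-entry wording lets the SAP count joints that 4.5.7.4 excludes. The net direction is not fixed. A reader might also want a percentage of bleeds missed. That would need per-joint rates that the documents do not give. The effect may be zero: it is so if no patient has a joint that is only unresolved and the looser wording adds none.

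The conclusion assumes that 2.3.2 is the definition that will be programmed. A fuller rule in a programming specification outside these documents would remove the error in practice, but not the need to align the SAP.

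**What to change.** - In SAP 2.3.2, adopt the definition in protocol 4.5.7.4: a major joint with at least 3 bleeds in the 24 weeks before study entry, or an unresolved target joint. State that status is determined once, at study entry.
- Refer to that definition in SAP 3.3.2.1 (target-joint ABR) and 3.3.3 (target-joint subgroup).
- Replace the version 2 synopsis in SAP Appendix 1 with that of version 3.
- Name the baseline source for unresolved status, joint by joint. Where history beyond the required 24 weeks is not available, report for how many patients this is so and label the result as based on the 24-week limb.

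The cost is a text revision and a check of the baseline data; no further models are needed. The drawback is that unresolved status rests on history older than the protocol requires, so it may be incomplete for some patients.
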